4.2 Study Drug Administration: Tivozanib

- 4.2.1 Drug Dispensing: The patient will be dispensed enough pills for 1 cycle at each monthly visit. Patient pill calendar will be reviewed by study coordinator or nurse. Pill count will be done, and any unused pills will be returned each cycle.
- 4.2.2 Dosing Schedule: Tivozanib hydrochloride will be administered orally, at a dose of 1.5 mg/day, beginning on Day 1 of Cycle 1. Subjects will receive tivozanib hydrochloride once daily for 3 weeks followed by 1 week off treatment. One cycle is defined as 4 weeks. Cycles will be repeated every 4 weeks in the absence of disease progression or unacceptable toxicities.
- 4.2.3 Dosing Information: The prescribed daily dose of tivozanib hydrochloride is to be taken, once per day, preferably in the morning, with water. Tivozanib should be taken on an empty stomach either 1 hour before or 2 hours after meals at the same time each day. The tablets should be swallowed whole and cannot be crushed or broken. Only one capsule of tivozanib hydrochloride should be taken each day. If a dose is vomited or otherwise missed that day for any reason, the dose for that day should not be made up. The next dose should be taken as prescribed at the next scheduled time (i.e., one capsule is to be taken even if the previous dose was vomited or otherwise missed; additional dose(s) should not be taken at any time to make up for any missed dose(s). Grapefruit and grapefruit juice should be avoided during the study.

In the event that tivozanib hydrochloride dosing is interrupted, the duration of cycle/treatment will not be extended; doses missed during the interruption will be captured as omitted rather than delayed.

4.2.4 Dosing Parameters: Subsequent cycles of therapy will not begin (day 1 of each cycle) until the ANC is ≥1500 cells/mcl and the platelet count is ≥ 100,000/mcl. Therapy will be delayed for a maximum of two weeks until these values are achieved. Patients who fail to recover adequate counts within a two week delay will be removed from study therapy. Grade 1 or 2 toxicity will not result in a dose reduction or treatment delay. Drug-related grade 3 or 4 toxicities will result in an interruption in treatment until the toxicity is less than or equal to grade 2. Additionally, a dose reduction will be performed. If there is no recovery to ≤ grade 2 or recurrent grade 3 or 4, then tivozanib will be discontinued.

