4.7.1 Tivozanib Hydrochloride Dose Modification

Clinical judgment will be used to determine appropriate management of the subject experiencing any adverse event (AE). The suggested criteria for dose modification for tivozanib hydrochloride drug-related AEs (excluding hypertension) are summarized in the table below.

Drug-Related	Action Taken	Subsequent Dosing Modification		
Adverse Events				
(excluding				
Hypertension ¹)				
Grade 1	No dose interruption, or reduction	None required; Dosing may continue		
	required; adverse event	at the same dose		
	management is at the discretion of			
	the Investigator			
Grade 2 No dose interruption, or reduction		None required; Dosing may continue		
	required; adverse event	at the same dose		
	management is at the discretion of			
	the Investigator			
Grade 3 ²	Interrupt dosing ³ until toxicity	Dosing may resume at same dose or		
	resolves to \leq grade 1.	reduced dose at the discretion of the		
		Investigator (see below for dose		
		reduction guidelines).		
Grade 4	Interrupt dosing until toxicity	Dosing may resume at same dose or		
	resolves to \leq grade 1.	reduced dose at the discretion of the		
	_	investigator (see below for dose		
		reduction guidelines).		

Tivozanib Hydrochloride Dose Modification Guidelines for Drug-Related Adverse Events

- 1. Hypertension must be treated as described in Appendix C prior to any dose modification
- 2. Referring to toxicity that persists despite appropriate medical care.
- 3. Tivozanib may be interrupted for up to 2 weeks. If a subject is able to resume treatment after an interruption of ≤ 2 weeks, missed doses will not be made up (i.e. the cycle duration will remain unchanged). If any drug related toxicity results in interruption of >2 weeks, the subject should be discontinued from study treatment unless there is clear benefit.

Patients should be followed for assessment of the toxicities until the AEs resolve or are deemed irreversible. The maximum delay of drug administration by the treating investigator or the patients' own decision for any reason, including toxicities, is 2 weeks. If the drug is withheld for more than 2 continuous weeks due to a treatment-related toxicity that does not resolve, the patient will be withdrawn from study treatment. The exception is HTN, which must first be treated as described in Appendix C prior to any dose modification.

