4.7.2 Tivozanib Hydrochloride Dose Reduction

Dose reductions of tivozanib hydrochloride to 1.0 mg/day will be allowed for subjects with \geq Grade 3 drug-related adverse events. The exception is hypertension, which must be treated with anti-hypertensive drugs prior to dose reduction. Once a subject's dose of tivozanib hydrochloride is reduced, it may not be re-escalated through the remainder of the subject's participation in the study. If a subject is unable to tolerate a reduced dose due to toxicities thought to be related to treatment, treatment should be discontinued.

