12.3 Appendix C: Management of Hypertension

RECOMMENDED MANAGEMENT FOR TIVOZANIB HYDROCHLORIDE-RELATED HYPERTENSION

Figure 1 provides a guideline for treatment of hypertension (HTN); however, changes may be made at the discretion of the treating physician.

RECOMMENDED ANTI_HYPERTENSIVE MEDICATIONS

Agent	Initial Dose	Intermediate Dose	Maximum Dose	
Dihydropyridine (DHP) Calcium Channel Blockers				
Nifedipine XL	30 mg po qd	60 mg po qd	90 mg po qd	
Amlodipine	2.5 mg po qd	5 mg po qd	10 mg po qd	
Felodipine	2.5 mg po qd	5 mg po qd	10 mg po qd	
Angiotensin Converting Enzyme (ACE)) Inhibitors			
Captopril	12.5 mg po tid	25 mg po tid	50 mg po tid	
Enalapril	5 mg po qd	10–20 mg po qd	40 mg po qd	
Ramipril	2.5 mg po qd	5 mg po qd	10 mg po qd	
Lisinopril	5 mg po qd	10–20 mg po qd	40 mg po qd	
Fosinopril	10 mg po qd	20 mg po qd	40 mg po qd	
Perindopril	4 mg po qd	None	8 mg po qd	
Quinapril	10 mg po qd	20 mg po qd	20 mg po qd	
Angiotensin II Receptor Blockers				
Losartan	25 mg po qd	50 mg po qd	100 mg po qd	
Candesartan	4 mg po qd	8–16 mg po qd	32 mg po qd	
Ibresartan	75 mg po qd	150 mg po qd	300 mg po qd	
Telmisartan	40 mg po qd	None	80 mg po qd	
Valsartan	80 mg po qd	None	160 mg po qd	

po = oral administration; qd = once daily; tid = three times daily

Adapted from Kollmannsberger C, et al, CUAJ. 2007; Vol 1 (Issue 2 Suppl):S41-54.

Management of Hypertension

Hypertension (HTN) that occurs during study treatment must be treated with anti-hypertensive drugs prior to any dose reduction. Recommended management of HTN for subjects receiving study drug is presented in Figure 1 (Appendix C).

Persistent HTN is defined as 2 consecutive elevated blood pressure (BP) measurements preferably taken in the clinic and obtained at least 1 hour apart. It is recommended that 24-48 hours should elapse between the decision steps. For a listing of recommended DHP (dihydropyridine) calcium channel blockers, angiotensin converting enzyme (ACE) inhibitors, and angiotensin receptor blockers, see Appendix C, Recommended Anti-hypertensive Medications.

Note: If a subject has controlled HTN on an anti-hypertensive regimen at baseline and then develops a worsening of HTN requiring more intensive therapy then the previous regimen, this would be considered Grade 3 HTN.

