Hypertension will be considered controlled if the following criteria are met: Diastolic blood pressure is reduced to less than 100 mmHg within 2 weeks of the initiation of anti-hypertensive treatment, confirmed by two consecutive blood pressure measurements at least 24 hours apart. Diastolic blood pressure does not increase by more than 20 mmHg subsequent to the start of anti-hypertensive treatment.

If subjects require a delay of >2 weeks for management of hypertension, discontinue protocol therapy. Subjects may have up to 2 drugs for management of hypertension prior to any dose reduction in tivozanib. 24-48 hours should elapse between modifications of antihypertensive therapy.

IRB #: STU00073756-CR0005 Approved by NU IRB for use on or after 12/17/2019 through 12/16/2020.

Northwestern University Study Number: NU12G11

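### Section 4.2.4 makes dose reduction, and discontinuation on recurrence, automatic for grade 3 or 4 toxicity without excepting hypertension, while 4.7 and Appendix C require antihypertensive drugs before any reduction

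*Combined protocol and SAP*

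**What the plan says.** Section 4.2.4 (Dosing Parameters) opens with blood-count thresholds for starting a cycle and then turns to toxicity in general: "Drug-related grade 3 or 4 toxicities will result in an interruption in treatment until the toxicity is less than or equal to grade 2". The next instruction is "Additionally, a dose reduction will be performed". The paragraph ends by requiring that tivozanib be stopped if the event does not recover to grade 2 or below, or on "recurrent grade 3 or 4, then tivozanib will be discontinued". It contains no exception for hypertension and no pointer to section 4.7 or Appendix C.

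Three other places treat hypertension separately:

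- Section 4.7.1 leaves hypertension out of its dose-modification table. Footnote 1 says "Hypertension must be treated as described in Appendix C prior to any dose modification", and the paragraph after the table repeats the exception.
- Section 4.7.2 allows reduction to 1.0 mg/day for related events of grade 3 or higher, then says "The exception is hypertension, which must be treated with anti-hypertensive drugs prior to dose reduction".
- Appendix C says "Hypertension (HTN) that occurs during study treatment must be treated with anti-hypertensive drugs prior to any dose reduction" and "Subjects may have up to 2 drugs for management of hypertension prior to any dose reduction in tivozanib". It also carries a grading note: "If a subject has controlled HTN on an anti-hypertensive regimen at baseline and then develops a worsening of HTN requiring more intensive therapy", the event counts as Grade 3.

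Sections 4.7.1 and 4.7.2 both forbid re-escalation after a reduction.

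**The concern.** For the same event, one section orders a reduction and the others make reduction a fallback after antihypertensive drugs. Section 4.2.4 is worded as a command and covers every related grade 3 or 4 event, so a site can follow it in good faith and lower a dose that the hypertension rules would have kept.

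The consequence for that patient is lasting. She cannot return to 1.5 mg. The cut also uses up the only lower dose the protocol offers, and 4.7.2 stops treatment in a patient who cannot tolerate it. Under 4.2.4 a second grade 3 episode ends treatment, even if drugs control it again. Hypertension is among the most frequent severe toxicities in the cited tivozanib studies, so the situation is foreseeable. What is at stake is consistent dosing and patient management across the four Northwestern sites.

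**Working it through.** There is no plan figure to reproduce. The check is a comparison of current text, with arithmetic for scale only.

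**1. The rules side by side, for related grade 3 hypertension**

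| Question | Section 4.2.4 | Sections 4.7.1, 4.7.2, Appendix C |
|---|---|---|
| Is the dose reduced? | Yes, automatically | Only after antihypertensive drugs; up to 2 may be used first |
| Recurrence at grade 3, controlled by drugs alone? | Discontinue | Not a stopping rule in the visible text |
| Recurrence needing a second reduction? | Discontinue | Withdraw unless the patient is judged to benefit (4.7.1) |
| Is treatment held? | Yes | Appendix C allows for a delay and stops therapy beyond 2 weeks |

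The first two rows conflict. The third nearly agrees. The fourth is not a clear conflict (see the objection).

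**2. A worked case**

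Exclusion 3.2.3 lets antihypertensive treatment be started or adjusted before entry, so treated and controlled patients can enrol. Suppose a patient enters on one drug, needs a second in cycle 1 for a related rise, and her pressure settles.

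- Under Appendix C she is on 2 drugs if the baseline drug counts, or 1 if it does not. Either way she is within the allowance and could stay at 1.5 mg.
- The Appendix C note labels the step-up Grade 3, so 4.2.4 read literally reduces her to 1.0 mg.

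**3. Size of the dose difference**

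Dose per 28-day cycle = 21 dosing days x daily dose.

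- At 1.5 mg: 21 x 1.5 = 31.5 mg.
- At 1.0 mg: 21 x 1.0 = 21.0 mg.
- Relative cut: (31.5 - 21.0) / 31.5 = 33%.

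**4. Scale among 30 patients**

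Expected cases = 30 x rate of grade 3 or higher hypertension, using the 1.5 mg/day studies in section 1.2.3:

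- Phase II renal-cell study: 32/272 = 11.8%; 30 x 0.118 = 3.5.
- ECG study in solid tumours: 9/50 = 18.0%; 30 x 0.18 = 5.4.
- Phase III renal-cell trial: 26%; 30 x 0.26 = 7.8.

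These count all grade 3 or higher hypertension. Patients not controlled on two drugs could be reduced under either rule, so those whom the rules treat differently are a subset. The documents do not give its size. The rates also come from other tumours and were graded under CTC version 3, while this trial uses CTCAE 4.03.

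**The case against.** The best defence is that the intended rule can be recovered. The hypertension exception is stated several times in 4.7.1, again in 4.7.2 and twice in Appendix C. Section 4.2.4 names no reduced dose; the 1.0 mg level is set in 4.7.2, and the exception follows it immediately, so a careful site would meet it. The amendment log records that 4.2.4 was moved from a former section on hematologic toxicity, which would explain the omission. Section 4.7 also leaves room for clinical judgment, and Appendix C for physician discretion.

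Most of this stands as evidence of intent. It does not put the exception into 4.2.4, whose wording is mandatory and not confined to blood counts. No clause ranks the sections, and section 11.7 requires the protocol to be followed exactly outside emergencies. Calling the 4.7.1 criteria suggested and the Appendix C figure a guideline leaves 4.2.4 as the firmer text. The specific rules also fix an order, drugs before reduction; none in the visible text says that a controlled event escapes the 4.2.4 cut. Figure 1 of Appendix C is not shown in the text available, so what it adds cannot be judged.

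Three stronger readings are tempting and are not supported:

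- *The sections also conflict on interruption.* Footnote 1 of 4.7.1 speaks of any modification, and its table treats a hold as one. But 4.7.2 and Appendix C speak of reduction, and Appendix C accepts a delay of up to 2 weeks. That conflict is not claimed.
- *Four to eight patients would be wrongly reduced.* Those are all expected severe cases, not the affected subset. Likewise, the chance of at least one such case at the lowest rate, 1 - (1 - 32/272)^30 = 0.977, is not the chance that the conflict arises.
- *The recurrence rules differ for everyone.* They differ only where drugs alone control the recurrence.

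**Conclusion.** The inconsistency is real and lies in current operative text. Section 4.2.4 makes reduction, and discontinuation on recurrence, mandatory for hypertension in cases where 4.7 and Appendix C would first treat with up to two drugs. For a patient whose hypertension drugs control, the two readings differ by 33% of the dose for the rest of her treatment.

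The number of such patients is unknown. The range of about 4 to 8 of 30 bounds it from above only at the cited rates, and assumes that those rates carry over to this population and grading version. The conclusion also assumes that a site might apply 4.2.4 as written; the intended rule is probably the specific one.

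A reader might infer that the efficacy result is compromised. The documents do not support that: the Simon two-stage rule, the 30-patient sample size and the response analysis in section 8 do not depend on this text. It is a dosing rule that should be corrected.

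**What to change.** In 4.2.4, directly after "Additionally, a dose reduction will be performed", insert: *(except for hypertension, where antihypertensive treatment under 4.7.2 and Appendix C comes first, and the dose is reduced only if hypertension is not controlled on up to 2 drugs)*.

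After the discontinuation sentence, add: *Recurrent grade 3 hypertension that is controlled by antihypertensive drugs does not by itself require discontinuation.*

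Leave the interruption rule for severe hypertension in place, subject to Appendix C and its 2-week limit. Exempting hypertension from interruption as well would remove the only mandatory hold for severe hypertension, including grade 4, in the visible text. Check the new wording against Figure 1 before issuing it.

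The cost is one phrase and one sentence in a protocol amendment, with the usual approval and distribution to sites. No assessment, sample size or analysis changes.

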4.3 General Concomitant Medication and Supportive Care Guidelines

- 4.3.1 Premedications for Study Drug-Related Toxicities
 - 4.3.1.1 Patients should not be premedicated prior to receiving the first dose of study drug.
 - 4.3.1.2 Thereafter, patients having experienced symptoms suggesting mild to moderate study drug administration-related reactions may be premedicated

with standard measures (eg, acetaminophen, diphenhydramine, H2-blockers, and/or dexamethasone), as clinically indicated.

- 4.3.1.3 Mandatory premedication will be recommended for all patients treated on this study should a pattern of mild to moderate study drug administration-related reactions begin to emerge.
- 4.3.1.4 Any medications administered for either prophylaxis or therapy of symptoms considered to be associated with study drug will be documented and reported. Subjects should avoid agents known to be weak Cytochrome P450 (CYP3A4) inducers or inhibitors for the duration of study treatment. See Appendix B for further information on Cytochrome P450 (CYP3A4) inducers and inhibitors.

4.3.2 Concomitant Medications

The following medications/treatments are prohibited during study treatment:

- 4.3.2.1 Chemotherapy, biological therapy (including cytokines, signal transduction inhibitors, monoclonal antibodies), immunotherapy or any other systemic therapy for ovarian, fallopian tube or primary peritoneal cancer.
- 4.3.2.2 Treatment with radiotherapy (including palliative)
- 4.3.2.3 Strong/moderate Cytochrome P450 (CYP3A4) inducers or inhibitors for the duration of study treatment. All CYP3A4 inducers and inhibitors should be used with caution (See Appendix B for further information).

Note: As this list is constantly evolving, if a medication is incorrectly documented as prohibited in this protocol, documentation from the site pharmacist to the contrary will be acceptable for the purposes of registration.

- 4.3.2.4 Subjects will NOT receive prophylactic growth factors [filgrastim (G-CSF), sargramostim (GM-CSF), pegfilgrastim (Neulasta)] unless they experience recurrent neutropenic complications after treatment modifications specified below.
- 4.3.2.5 Subjects will NOT receive prophylactic thrombopoietic agents.
- 4.3.2.6 Subjects may not receive erythropoietin (EPO) but may receive iron supplements, and/or transfusions as clinically indicated for management of anemia.
- 4.3.3 The following medications/treatments are permitted during the study treatment:
 - 4.3.3.1 Full dose oral anticoagulants and/or anticoagulation with low molecular weight heparin or unfractionated heparin administered subcutaneously. Subjects taking anticoagulants should have their coagulation panels monitored as scheduled during the study and as clinically indicated.
 - 4.3.3.2 Subjects are permitted to receive supportive care throughout the study including transfusions (blood, blood products), antibiotics, anti-emetics, anti-diarrheal agents, analgesics, or bisphosphonates, when appropriate, with the exception of any prohibited medications/treatments.
- 4.3.4 Other medications/treatments that should be avoided during the study treatment:

- 4.3.4.1 Herbal remedies should be avoided; however, if herbal remedies are used, they should be documented as a concomitant medication.
- 4.3.4.2 Medications/agents known to prolong QT interval.
- 4.3.5 Systemic hormonal therapy, with the exception of:
 - 4.3.5.1 Hormonal therapy for appetite stimulation or contraception;
 - 4.3.5.2Nasal, ophthalmic, inhaled and topical steroid preparations;
 - 4.3.5.3 Hormone replacement therapy for conditions such as adrenal insufficiency, hypothyroidism, etc.;
 - 4.3.5.4Low dose maintenance steroid therapy (equivalent of prednisone ≤ 10 mg/day) for other conditions.

4.4 Duration of Therapy

Patients may continue to receive cycles of treatment until any of the following occur:

- Disease progression
- Development of an inter-current illness that prevents further administration of treatment
- Unacceptable adverse event(s)
- Patient decides to withdraw from either study treatment or the study as a whole
- The treating investigator determines that the patient should be taken off treatment for any reason (i.e. changes in condition, inability to comply with study treatment or procedures)

4.5 Duration of Follow Up

Patients will return for an end of treatment visit within ± 14 days of the decision to discontinue treatment.

Subjects will be followed approximately 30 days after discontinuation of treatment and then approximately every 3 months for 2 years and then approximately every 6 months for 3 years after removal from study or until death, whichever occurs first. Subjects will be monitored for survival for this 5-year period. Subjects removed from study for unacceptable adverse event(s) will be followed until resolution or stabilization of the adverse event.

4.6 Removal of Subjects from Study Treatment and/or Study as a Whole

Patients can be taken off the study treatment and/or study as a whole at any time at their own request, or they may be withdrawn at the discretion of the investigator for safety, behavioral or administrative reasons. The reason(s) for discontinuation must be clearly documented on the appropriate eCRF and may include:

- Patient voluntarily withdraws from treatment (follow-up permitted)
- Patient withdraws consent (no follow-up permitted)
- Patient is unable to comply with protocol requirements
- Patient demonstrates disease progression
- Patient experiences unacceptable toxicity

- Treating physician determines that continuation on the study would not be in the patient's best interest
- Patient becomes pregnant
- Patient develops a second malignancy that requires treatment which would interfere with this study
- Patient becomes lost to follow-up (LTF)

4.7 Dose Delays/Dose Modification

Comprehensive assessments of any toxicity experienced by the patient will be performed throughout the course of this study. Anticipated toxicities that may be experienced are detailed in the section on adverse events in prior studies of tivozanib. Grades of toxicity (NCI Common Terminology for Adverse Events [CTCAE- Version 4.03]), as well as clinical judgment, will be used to determine appropriate management of the patient experiencing any adverse event while participating in this study. Any adverse event, whether observed by the investigator, or observed or experienced by the patient, will be reported. All clinical and laboratory adverse events must be carefully evaluated for severity, duration and relationship to tivozanib.

